#### Generally,

- thirst, frequent urination, and sweet breath may occur with blood ketones <1.0 mmol/L (small/moderate urine ketones),
- dry mouth, nausea, stomach cramps, and/or vomiting may occur with blood ketones from 1.0 to 3.0 mmol/L (moderate/large urine ketones),
- labored deep breathing, extreme weakness, confusion, and eventually unconsciousness (coma) may occur with blood ketones >3.0 mmol/L (large urine ketones)

The study site personnel must also educate the subject on the importance of measuring capillary blood ketone (or urine ketones) regardless of the concomitant glucose levels, as these may be not as elevated (ie, >250 mg/dL [>13.9 mmol/L]) as usually observed during DKA.

Also, the subject must be instructed when to call the study site and what action to take while awaiting further instructions and when to seek immediate medical attention. In particular, in the presence of blood ketones ≥0.6 mmol/L (repeated and confirmed), subjects are required to:

- contact the study site to receive further instructions based on the clinical assessment of the investigator or delegate
- interrupt study drug

- increase insulin if subject is on insulin (without increasing risk of hypoglycemia)
- increase carbohydrate and fluid intake
- seek immediate medical attention if appropriate increases in insulin and fluid intake cannot be managed by the subject (due to hypoglycemia, vomiting etc) and/or the subject shows signs/symptoms of DKA such as nausea, vomiting, abdominal pain, dehydration, or rapid breathing

## Management of insulin and food intake during illness and/or in presence of elevated ketone levels

Subjects who are on insulin must be instructed to NOT reduce or interrupt insulin treatment during sick days and/or in the presence of ketone elevations, even if they are vomiting and unable to eat. Subjects should be educated on the importance of increasing insulin and carbohydrates in the presence of elevated ketones, unless there is increased risk of hypoglycemia (eg, reduced glucose levels in subject who is vomiting). If the subject is unable to increase insulin in the presence of elevated ketones due to fear of hypoglycemia, the subject should seek immediate medical attention.

Subjects should be instructed to eat small meals and to eat more frequently when they are ill. Soft foods or liquids are often tolerated best. Fluid intake is essential during illness. If vomiting, diarrhea, or fever is present, the subject should be instructed to take small quantities of liquids every 15 to 30 minutes. Clear broth, tea, or other fluids can supplement liquids containing carbohydrate. Eating about 10 to 15 g carbohydrate every 1 to 2 hours is usually sufficient. Foods and beverages containing about 15 g carbohydrate that can be considered for subjects include:

½ cup (~ 125 mL) regular gelatin ½ cup (~ 125 mL) ice cream ½ cup (~ 125 mL) custard 1 regular double Popsicle ¾ cup (~ 200 mL) regular ginger ale  $\frac{1}{2}$  cup (~ 125 mL) regular soft drink  $\frac{1}{2}$  cup (~ 125 mL) orange or apple juice 1 cup (~ 250 mL) Gatorade 1 cup (~ 250 mL) creamed soup

## Attachment 2: Suggested Algorithm for Ketone Monitoring and Findings of Elevated Ketones

Subjects will be instructed to measure capillary blood ketone levels:

- any time the subject is ill or does not feel well
- subject has undergone a minor procedure (eg, dental extraction)
- anytime a possible cause for ketonemia has occurred that would predispose the subject to DKA (eg, skipping insulin dose, strenuous physical exercise, reduced carbohydrate intake)

Ketone measurements during periods of increased risk of ketonemia/ketonuria must be obtained regardless of the concomitant blood glucose values; ketone measurements should preferably be done prior to dosing to allow prompt interruption of study drug, if required. Ketone should be measured until the etiology for measuring ketones has abated (eg, illness has subsided).

#### **Instructions for Elevated Ketone Findings**

- If **blood ketone** ≥0.6 mmol/L (with or without symptoms, regardless of concomitant glucose levels) confirmed by repeat assessment (suggested repeat measurement one hour later or sooner if in presence of symptoms), the subject should be instructed to:
  - contact the investigator or qualified assigned designee immediately (if possible)
  - if dose of study drug has not yet been taken, skip that dose and resume, with the permission of the investigator or qualified site personnel, once blood ketone levels are <0.6 mmol/L and precipitating cause (if identified) has resolved
  - if subject is on prandial insulin, increase insulin every 2 to 3 hours until the blood ketones have decreased to <0.6 mmol/L

  - continue monitoring blood glucose
  - increase carbohydrate and fluid intake to allow increased insulin dosing if on insulin treatment
  - continue monitoring blood ketones at least every 4 to 6 hours until ketone levels reach levels
     ≤0.2 mmol/L

The investigator or qualified assigned designee should review the potential precipitating factors with the subject, and correct if necessary

- Illness/infection
- Reduction or missed insulin dose
- Reduction in carbohydrate intake or fasting
- Alcohol consumption
- Strenuous exercise
- Significant stress
- In female subjects, phase of menstrual cycle

Subjects are to be instructed to *SEEK IMMEDIATE MEDICAL ATTENTION* in the presence of blood ketones ≥0.6 mmol/L, regardless of blood glucose levels, IF:

• appropriate increases in insulin and/or fluid intake cannot be managed by subject (due to hypoglycemia, vomiting etc)

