# 9.2.1.2. Ketone Measurements During Periods of Increased Risk of Ketonemia

It is paramount that subjects and parents/legal guardians are educated on obtaining ketone measurements whenever they experience potential causes of ketone elevation that might lead to ketoacidosis if not identified and treated in time.

These possible precipitating factors include, but are not limited to:

- Acute illness
- Significant and/or sudden reduction in insulin dose (eg, non-compliance with insulin treatment regimen)
- Prolonged fasting or low carbohydrate diet
- Dehydration and/or a marked increase in physical activity
- Increased alcohol consumption
- Undergoing a minor procedure (eg, dental extraction)
- Significant physiologic stress

Subjects and parents/legal guardians will be instructed to test their ketone levels in the presence of these possible precipitants, regardless of the presence of symptoms of DKA (such as nausea, abdominal pain, dehydration, polyuria), as these are nonspecific and might be interpreted as gastroenteritis, or signs and symptoms of osmotic-diuresis related to the use of study drug. In addition, it is paramount to instruct subjects and parents/legal guardians to test ketones in such occasions regardless of the concomitant glucose level, as blood glucose might be incongruously low (<250 mg/dL [<13.9 mmol/L]) and not as high as one would expect to observe during ketosis and DKA.

Ketone measurements performed during illness or periods of increased risk of ketone elevation, should preferably be done *prior* to dosing of study drug to allow prompt interruption of study drug, if required.

During sick days, subjects must refer to the algorithm (see Attachment 2, Suggested Algorithm for Ketone Monitoring and Findings of Elevated Ketones) to determine, based on severity of illness, degree of ketosis, and ability to increase insulin dose and food intake, the appropriate frequency of retesting of ketones and glucose, action with blinded study drug, need to seek immediate medical attention, or to contact the study site.

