# • the subject shows signs/symptoms of DKA such as nausea, vomiting, abdominal pain, dehydration, or rapid breathing

It should be noted that these recommendations are provided as guidance to subjects and investigators. Investigators are expected to use their clinical judgment and knowledge of the subject's medical history and assessment of present condition.

Whenever possible, the management should be based on capillary blood ketone levels. Only in those rare instances in which capillary blood ketones cannot be obtained, a urine ketone levels may be used. A urine ketone level of moderate/large may be considered an approximation of blood ketone level of 0.6 mmol/L. It should be noted however, that in the presence of dehydration, urinary ketone measurements may be difficult to obtain and may not provide reliable readings.

For any confirmed ketone level  $\geq 0.6$  mmol/L that triggers the above actions, the subject will be requested to enter detailed information in the subject diary, including (but not limited to) ketone and glucose values, precipitating factors (eg, changes in insulin dose regimen, illness), and treatment received.

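### Attachment 2's sick-day guidance allows 1 to 2 repeat prandial insulin increases before the next required ketone reading, sets no glucose interval, and leaves Attachment 1's hypoglycemia caveat out of the increase step

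*Protocol*

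**What the plan says.** Attachment 2 (Instructions for Elevated Ketone Findings) applies once a blood ketone value of at least 0.6 mmol/L has been confirmed by a repeat, whatever the glucose level. Its relevant steps are:

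- Insulin: "if subject is on prandial insulin, increase insulin every 2 to 3 hours until the blood ketones have decreased to" below 0.6 mmol/L.
- Glucose: "continue monitoring blood glucose", with no interval.
- Ketones: "continue monitoring blood ketones at least every 4 to 6 hours until ketone levels reach levels" of 0.2 mmol/L or lower.

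The page also asks for immediate contact with the investigator or designee if possible, for more carbohydrate and fluid, and for immediate medical attention if the insulin increases cannot be managed, with hypoglycemia named as one reason. Its status is stated: "It should be noted that these recommendations are provided as guidance to subjects and investigators". Investigators are expected to apply clinical judgment.

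Section 9.2.1.2 says that on sick days subjects must consult this algorithm to determine, among other things, "the appropriate frequency of retesting of ketones and glucose". The same sentence makes that depend on how ill the subject is, how far ketosis has gone, and whether insulin and food can be increased.

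Attachment 1 covers the same action at the same ketone level, with a condition: "increase insulin if subject is on insulin (without increasing risk of hypoglycemia". Its part on insulin and food intake repeats the condition in other words. The increase step in Attachment 2 carries no such condition.

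**The concern.** The insulin step has a stop rule that depends on a measurement, but the action is scheduled more often than the measurement. Someone who follows each line at its stated minimum repeats the increase at least once without a new ketone value, so an increase can be made after ketones have already fallen below the stop level. The page does not require a current glucose value before an increase either, and it gives no glucose frequency, although Section 9.2.1.2 sends subjects there for one. Section 9.3 does not fill the gap: its double-blind-phase minimum is fasting self-monitoring on 3 days per week.

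The protocol itself explains why glucose matters here. Section 3.2 expects that subjects taking insulin with canagliflozin may need less insulin to avoid hypoglycemia, and warns that ketoacidosis can occur with glucose below 250 mg/dL. Insulin increases may therefore start without marked hyperglycemia. The readers of the page are ill children and adolescents and their families at home. What is at stake is avoidable hypoglycemia risk.

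**Working it through.** The plan gives no figure of its own to reproduce. The check counts intervals.

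**Inputs, all from Attachment 2**
- Interval between insulin increases, d: 2 to 3 hours.
- Longest interval to the next required ketone reading, T: 4 to 6 hours.
- Required glucose interval: none stated.

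**Assumptions.** The first increase is made at the confirmed reading (time 0), and the clock for the next required reading starts then. If an increase and a required reading fall at the same hour, the reading is taken first.

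**Formula.** Repeat increases fall at d, 2d, 3d and so on. The number made before the required reading is the count of k = 1, 2, … with k × d < T, which equals ceil(T/d) − 1.

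| T (hours) | d = 2 h | d = 2.5 h | d = 3 h |
|---|---|---|---|
| 4 | 1 | 1 | 1 |
| 5 | 2 | 1 | 1 |
| 6 | 2 | 2 | 1 |

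For example, T = 6 and d = 2 gives 6/2 − 1 = 2 (at 2 and 4 hours). T = 4 and d = 3 gives ceil(1.33) − 1 = 1 (at 3 hours). Across the stated intervals the result is 1 to 2, and it is never 0, because the longest d (3 hours) is shorter than the shortest T (4 hours).

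**Sensitivity to the tie rule.** If an increase due at the same hour as the reading is also counted, the range is 1 to 3; the 3 arises at T = 6 and d = 2.

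**With a reading required before each repeat increase.** T equals d, so the count is ceil(1) − 1 = 0.

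**Caveat, side by side.** Attachment 1 conditions the insulin increase on not raising hypoglycemia risk, and says so twice. Attachment 2, which alone sets the repeat schedule, does not put that condition on its increase step. It deals with hypoglycemia indirectly, through carbohydrate intake, glucose monitoring and the immediate-care trigger.

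**The case against.** The strongest reply is that the count treats a floor as the working interval. The ketone line is a minimum and runs on to 0.2 mmol/L, so it also has to cover the period after increases have stopped. The word until in the insulin step can be obeyed only by measuring. Section 9.2.1.2 individualises retest frequency, and the page is labelled guidance. The hypoglycemia caveat is already in Attachment 1, which is used in the same counseling.

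There are also real safeguards:
- Site contact is asked for in Section 9.2.2 and both attachments, and Section 9.2.2 expressly includes insulin dose adjustment. The study card carries a 24-hour number (Section 12.2.1).
- Attachment 1 advises about 10 to 15 g of carbohydrate every 1 to 2 hours during illness.
- Glucose, insulin dose and dose changes are to be entered in the diary (Section 9.2.1.2). Fingersticks are asked for at possible hypoglycemic episodes (Section 9.8).
- Immediate care is required if increases cannot be managed.

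Most of this stands, and it limits the weight of the point. It does not close the gap, because none of these provisions requires a ketone or glucose reading before the next increase. The diary entry may use the glucose value closest in time, and the immediate-care trigger responds to a problem that has already arisen.

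A reader might infer that the plan directs families to dose without testing, or that it has no hypoglycemia caveat. Neither is supported: earlier testing is open to them, and the caveat is absent from one step only.

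**Conclusion.** The point holds as a minor, cheaply corrected patient-safety matter. At the page's stated minimum, 1 to 2 repeat increases can precede the next required ketone reading. No glucose interval is given where Section 9.2.1.2 says one is to be found, and the increase step lacks a condition that the sponsor wrote elsewhere for the same action. The count rests on the first increase being made at the confirmed reading and on testing at the minimum frequency. It describes what the wording permits, not what families will do.

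Three larger claims might be inferred and should not be. First, a percentage of increases made without a reading over a whole episode: the documents give no episode length, and the share shifts with the intervals chosen inside the stated ranges. Second, a number of hypoglycemic events or affected subjects: neither the size of each increase nor the rate of confirmed ketone episodes is given, and hypoglycemia depends on glucose and dose rather than on the ketone count. Third, an effect on the HbA1c comparison: nothing in the documents supports one. The point is confined to subjects on prandial insulin with confirmed ketones of at least 0.6 mmol/L.

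**What to change.** In Attachment 2, and in the matching subject counseling material:

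1. Check ketones and glucose before each repeat insulin increase, and repeat the increase only if ketones are still at or above 0.6 mmol/L.
2. Once ketones are below 0.6 mmol/L, stop the increases and check ketones at least every 4 to 6 hours until they are 0.2 mmol/L or lower.
3. Add Attachment 1's hypoglycemia condition to the increase step.

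The guidance status, the site-contact and immediate-care rules, and the urine-ketone fallback stay as they are. Needed insulin is not withheld merely because ketones are slow to fall, since increases continue while ketones stay at or above the threshold; if hypoglycemia prevents an increase, the existing route to immediate care applies.

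The cost is more fingersticks for an ill child while increases continue. Ketone checks would come every 2 to 3 hours in place of a minimum of every 4 to 6 hours, which is between 4/3 ≈ 1.3 and 6/2 = 3 times the present minimum, with glucose measured at the same times. Testing supplies are already provided as necessary (Time and Events Schedule, footnote u). The revised attachment and counseling material need IEC/IRB review (Sections 16.2.2 and 17.1), which can be bundled with the next amendment.

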#### Recognition of signs and symptoms of DKA

The study site personnel must ensure that the subject and parents/guardians are educated on recognizing signs and symptoms of DKA (ie, nausea, vomiting, abdominal pain, increased urination and thirst, fruity-smelling breath, rapid, deep respirations, headache, somnolence, etc). It is fundamental that in the presence of these signs/symptoms concomitant ketone levels are obtained to determine the proper actions and course of treatment, given that many of the signs/symptoms of DKA are nonspecific (eg, gastrointestinal symptoms) and may vary with degree of ketone elevation.

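### Above the 0.6 mmol/L action level, no ketone value by itself sends a child to urgent care; one added line at 3.0 mmol/L would close a narrow gap

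*Protocol*

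**What the plan says.** Protocol Section 9.2.1.2 sends subjects on sick days to Attachment 2. There they are to decide, "based on severity of illness, degree of ketosis, and ability to increase insulin dose and food intake", several things: how often to retest, what to do with study drug, and the "need to seek immediate medical attention, or to contact the study site".

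Attachment 2 (Instructions for Elevated Ketone Findings) has one action level, a reading of at least 0.6 mmol/L confirmed by repeat. The subject then contacts the investigator, with a proviso that this be possible. The other steps are to skip an untaken dose, raise prandial insulin if used, take more carbohydrate and fluid, and retest at least every 4 to 6 hours. Urgent care applies "in the presence of blood ketones ≥0.6 mmol/L, regardless of blood glucose levels, IF" insulin and/or fluid increases cannot be managed, or DKA signs appear.

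Attachment 1 states its steps under the words "in the presence of blood ketones ≥0.6 mmol/L (repeated and confirmed), subjects are required to". Its urgent-care line is to "seek immediate medical attention if appropriate increases in insulin and fluid intake cannot be managed by the subject", or if DKA signs appear. It adds that a subject who cannot raise insulin for fear of hypoglycemia should get immediate care. Attachment 1 also lists three ketone bands (below 1.0, 1.0 to 3.0, above 3.0 mmol/L), but only to describe the symptoms that may go with each.

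Section 3.2 says that hyperketonemia can be defined as above 1.0 mmol/L and DKA as above 3.0 mmol/L.

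**The concern.** The attachments hold the protocol's written DKA safeguard for children treated at home. Section 3.2 warns that the drug may keep glucose lower than expected in DKA and so delay its recognition. Section 9.2.1.2 wants ketones tested whether or not DKA symptoms are present, "as these are nonspecific and might be interpreted as gastroenteritis, or signs and symptoms of osmotic-diuresis related to the use of study drug". Attachment 1 says that when such symptoms occur, "concomitant ketone levels are obtained to determine the proper actions and course of treatment".

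The meter value is the signal that does not depend on reading symptoms correctly. Yet once 0.6 mmol/L is passed, a higher number changes no written action. A family that follows the attachments exactly could keep a child at home with a reading in the range that Section 3.2 associates with DKA, if the site does not answer and nobody recognises the symptoms. At stake is a delay in treatment for that child.

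**Working it through.** No calculation applies. The check is to run a case through the written rules.

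**Case.** A confirmed reading of 3.5 mmol/L (an illustrative value above 3.0), no recognised DKA symptoms, insulin and fluids manageable, site not reached.

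| Step | Source | Result |
|---|---|---|
| Is the reading at least 0.6? | Attachments 1 and 2 | Yes (3.5 ≥ 0.6) |
| Are insulin or fluid increases unmanageable? | Attachments 1 and 2 | No |
| Does fear of hypoglycemia prevent an insulin increase? | Attachment 1, insulin and food section | No |
| Are DKA signs or symptoms present? | Attachments 1 and 2 | None recognised |
| Does the >3.0 band carry an action? | Attachment 1 | No, symptoms only |
| Is there a fallback if the site is not reached? | Attachments 1 and 2, Section 9.2.2 | None given |

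The result is no instruction to seek urgent care. Replacing 3.5 by 0.6 changes no row except the band, so the written actions are the same at both values, including the 4 to 6 hour retest.

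**Changing one condition at a time.**

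- Site reached: Section 9.2.2 has the site advise on the possible need for urgent care. The case is covered.
- Vomiting, abdominal pain or rapid breathing present: urgent care is triggered at any reading of 0.6 or more. Covered.
- Insulin or fluids not manageable: urgent care is triggered. Covered.
- Reading between 0.6 and 3.0: the rule is the same, but the level is below the value that Section 3.2 links to DKA.

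The gap therefore needs all four conditions together.

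**Consistency with Section 9.2.1.2.** That section names three inputs that jointly settle several outputs. Degree of ketosis is used, as the 0.6 threshold in front of every action. The section promises neither graded tiers nor a value that acts alone.

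**Wording across the attachments.** The urgent-care line in Attachment 1 joins insulin and fluid with *and*; Attachment 2 uses *and/or*. Attachment 2's carbohydrate and fluid line ends with a qualifier about insulin treatment. It could limit the whole line to insulin users, or only explain why insulin users need the carbohydrate. Attachment 1 has no such qualifier.

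**The case against.** The strongest defence is that the chosen rule acts early. At 0.6 mmol/L, one fifth of 3.0 (0.6/3.0 = 0.2), nausea alone is enough to send a child to care, and the symptom list is open-ended. Site contact is required at every confirmed reading, Section 12.2.1 puts a 24-hour number on the study card, and retesting gives new symptoms a chance to trigger the rule. Section 9.2.1.2's remark on misread symptoms explains why to test. A family that suspects gastroenteritis is still sent to care once the reading is 0.6 or more. All of this stands, and it is why the gap is small. The misreading argument survives mainly for thirst and frequent urination put down to the drug.

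It is also fair that 3.0 mmol/L is not the protocol's DKA case definition. Section 10.2.1 uses biochemically confirmed DKA, with low pH as an example, and SAP Section 6.1.1 summarises adjudicated events. The action level is a clinical choice, and Section 3.2 makes 3.0 the natural candidate. Attachment 2 calls itself guidance subject to the investigator's judgment, but that judgment helps only once contact is made.

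Two stronger readings are tempting. One is that Attachment 2 contradicts Section 9.2.1.2; as shown above, it does not. The other is to size the gap from the adult counts in Section 3.2: of 1,297 subjects, 22 (1.70%) had total ketones of at least 3.0 mmol/L and 6 (0.46%) of at least 5.0. Those counts cover any such rise, in one study of Japanese adults, and nearly all such readings would already be covered here. They also measure total ketones, whereas the meter reads the fraction that Section 9.2 puts at about 75%. They do not measure the uncovered case.

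**Conclusion.** The point holds as a cheap, minor patient-safety improvement. The attachments lack a value-based backstop for a child whose ketones exceed 3.0 mmol/L when symptoms go unrecognised, insulin and fluids are manageable, and the site is not reached. Attachment 2 foresees the last condition and gives no fallback.

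The case should be rare, since all four conditions must coincide, but its frequency cannot be estimated from the documents. In the adult study the rises were transient and no subject developed DKA. Nothing here touches endpoints, sample size or analysis.

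The conclusion rests on the protocol and its attachments. The subject diary and counselling materials are not among the documents and may already contain such an instruction.

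**What to change.** Add one line to Attachments 1 and 2: *Blood ketones above 3.0 mmol/L: get immediate medical attention regardless of symptoms or glucose, whether or not the site has been reached.* Section 9.2.1.2 can stand.

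Optional editorial alignment: use *insulin and/or fluid* in Attachment 1's urgent-care line, and make clear in Attachment 2 that the carbohydrate and fluid increase applies to all subjects, as in Attachment 1.

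The cost is a wording change in two attachments and in any family materials drawn from them, plus an occasional extra urgent visit for transient ketonemia in either arm. Visits and data collection stay as planned.
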